**Proprietary confidential information.**

**© 2016 Boehringer Ingelheim International GmbH or one or more of its affiliated companies. All rights reserved.**  
This document may not - in full or in part - be passed on, reproduced, published or otherwise used without prior written permission.

		•
Rationale for change		
Change 1: Based on review of recently published cardiovascular outcome trials, changing the protocol definitions of the primary and secondary endpoints, essentially substituting 4-Point MACE (Cardiovascular (CV) Death, Non-Fatal Stoke, Non-fatal Myocardial Infarction and Hospitalization for Unstable Angina) with 3-Point MACE (CV Death, Non-Fatal Stoke, Non-fatal Myocardial Infarction). eGFR cut off changed in response to the NIH/FDA scientific workshop on GFR decline as an endpoint for clinical trials in CKD and the current clinical landscape on decline in estimated glomerular filtration rate and subsequent risk of end stage renal disease and mortality.

Section to be changed		
7.3.4 Interim analyses

Description of the change		Interim analyses removed
Rationale for change		
Based on observed event rates, the time interval between interim and final analyses is estimated to be around nine months. This time interval is too short to make meaningful differences to trial conduct, especially as the overall objective is to ensure adequate exposure to study drugs to characterise cardiovascular, renal and overall safety profile

Section to be changed		
7.6 Determination of sample size

Description of change		
Assuming the hazard over time in patients on linagliptin is the same as in patients on placebo (hazard ratio (HR): <math>\lambda</math> linagliptin/<math>\lambda</math> placebo =1), 625 patients with events will deliver an overall power of 90% in a test to demonstrate

Proprietary confidential information.

© 2016 Boehringer Ingelheim International GmbH or one or more of its affiliated companies. All rights reserved.

This document may not - in full or in part - be passed on, reproduced, published or otherwise used without prior written permission.

	
non-inferiority of linagliptin vs. placebo within the pre-specified non-inferiority (NI) margin of 1.3 for the HR; at the overall 1-sided <math>\alpha</math>-level of 2.5% and with one interim analysis at <math>\alpha=1.0\%</math> after 70% of the events (calculated with East, version 5.4). Assuming a study duration of 3.8 years, recruitment within 3 years and a cumulative lost to follow-up rate of 2.0%, 4150 patients per group are required to achieve 625 patients with a primary endpoint
 
Was changed into:
 
Assuming the hazard over time in patients on linagliptin is the same as in patients on placebo (hazard ratio (HR): <math>\lambda</math> linagliptin/<math>\lambda</math> placebo = 1), 611 patients with events will deliver an overall power of 90% in a test to demonstrate non-inferiority of linagliptin vs. placebo within the pre-specified non-inferiority (NI) margin of 1.3 for the HR; at the overall 1-sided <math>\alpha</math>-level of 2.5% (calculated with East, version 5.4)

Rationale for change	The change of the primary variable does not affect the required number of patients with event; the slight reduction from 625 to 611 patients is due to the elimination of the interim analysis. Since the event rate is higher than initially assumed the same power can be achieved within the originally planned timelines with a sample size of approximately 7000 patients.
Section to be changed	8. Informed consent, data protection, trial records
Description of change	
Insurance Cover: The terms and conditions of the insurance cover are made available to the investigator and the patients via documentation in the ISF (Investigator Site File).
 
Was changed into:
 
The certificate of insurance cover is made available to the Investigator and the patients, and is stored in the ISF.

Section to be changed	9.2. Unpublished references
Description of change	Author of IB omitted
Rationale for change	Change in authorship
Rationale for change	For clarification
Section to be changed	10.3 Blood pressure measurement procedure
Description of change	
Change 1:
 
.....If an electronic blood pressure device is used the pulse rate at time of the second blood pressure reading may be used.
 
Was changed into:
 
.....If an electronic blood pressure device is used the pulse rate at time of the second blood pressure reading


Proprietary confidential information.

© 2016 Boehringer Ingelheim International GmbH or one or more of its affiliated companies. All rights reserved.

This document may not - in full or in part - be passed on, reproduced, published or otherwise used without prior written permission.

		should be used.  In addition the following wording was added in the last paragraph: the mean value should be recorded in the eCRF.
Rationale for change		Change 1: For clarification
Section to be changed		10.4 silent myocardial infarction
Description of change		Definition of silent MI requires no preceding clinical history of MI (including stent thrombosis and other coronary events) and investigator reporting of silent MI
Rationale for change		Clarification added

Proprietary confidential information.

© 2016 Boehringer Ingelheim International GmbH or one or more of its affiliated companies. All rights reserved.  
This document may not - in full or in part - be passed on, reproduced, published or otherwise used without prior written permission.

### 2. LIST OF ABBREVIATIONS

Include a list of all abbreviations used in the TSAP

Term	Definition / description		
------	--------------------------	--	--

ATC Anatomical-Therapeutic-Chemical

CEC Clinical Event Committee

CI Confidence Interval

CKD Chronic Kidney Disease

CRA Clinical Research Associate

CTMF Clinical Trial Master File

CTP Clinical Trial Protocol

CTR Clinical Trial Report

CV Cardiovascular

DBL Data Base Lock

DBP Diastolic Blood Pressure

ECG Electrocardiogram

eCRF Electronic Case Report Form

EMA European Medicines Agency

EOT End Of Treatment

Term
------

HbA1c Glycosylated Haemoglobin

HR Hazard Ratio

IC Informed Consent

ICH International Conference on Harmonisation

IQR Interquartile Range

IRT Interactive Response Technology

ISF Investigator Site File

ITT Intent To Treat

KDIGO Kidney Disease Improving Global Outcomes

KM Kaplan-Meier

LTFU Lost To Follow Up

MACE Major Adverse Cardiovascular Events

MedDRA Medical Dictionary for Regulatory Activities

MI Myocardial Infarction

OR Odds Ratio

PPS Per Protocol Set

PT Preferred Term

pt-yrs Patient-years

PV Protocol Violation

Q1 Lower quartile

Q3 Upper quartile

Term	Definition / description
RS	Randomized Set
REML	Restricted Maximum Likelihood
SAE	Serious Adverse Event
SBP	Systolic Blood Pressure
SCR	Screened Set
SD	Standard Deviation
SDG	Standardized Drug Grouping
SGLT	Sodium Glucose Linked Transporter
SMQ	Standardized MedDRA Query
SOC	System Organ Class
T2DM	Type 2 Diabetes Mellitus
TEAE	Treatment Emergent Adverse Events
TIA	Transient Ischemic Attack
TNM	Tumor Node Metastasis
TS	Treated Set
TSAP	Trial Statistical Analysis Plan
UACR	Urine Albumin Creatinine Ratio
ULN	Upper Limit of Normal
VEGF	Vascular Endothelial Growth Factor
WHO-DD	World Health Organization Drug Dictionary
WHO-DD	World Health Organization Drug Dictionary

#### 3. INTRODUCTION

As per ICH E9, the purpose of this document is to provide a more technical and detailed elaboration of the principal features of the analysis described in the protocol, and to include detailed procedures for executing the statistical analysis of the primary and secondary variables and other data.

This Trial Statistical Analysis Plan (TSAP) assumes familiarity with the Clinical Trial Protocol (CTP), including Protocol Amendments. In particular, the TSAP is based on the planned analysis specification as written in CTP Section 7 "Statistical Methods and Determination of Sample Size". Therefore, TSAP readers may consult the CTP for more background information on the trial, e.g., on trial objectives, trial design and population, treatments, definition of measurements and variables, planning of sample size, randomisation.

This TSAP will be used for the final analysis only.

**CTP:** The primary objective is to demonstrate non-inferiority (by means of comparing the upper limit of a two-sided 95% confidence interval (CI) with the non-inferiority margin of 1.3) of treatment with linagliptin in comparison to placebo (as add-on therapy on top of standard of care) with respect to time to first occurrence of any of the adjudicated components of the primary cardiovascular (CV) composite endpoint (i.e. CV death, non-fatal stroke or non-fatal myocardial infarction (MI)) in patients with type 2 diabetes mellitus (T2DM).

If non-inferiority has been demonstrated, then the primary CV composite endpoint will be tested for superiority and the other objective, to assess the impact of treatment with respect to the composite renal endpoint (i.e. renal death, sustained end-stage renal disease (ESRD), sustained decrease in estimated glomerular filtration rate (eGFR)  $\geq$  40% from baseline), will be investigated separately with a test on superiority.

SAS® Version 9.4 (or later version) will be used for all analyses.

#### 4. CHANGES IN THE PLANNED ANALYSIS OF THE STUDY

The revisions of the protocol, up to including version 3.0 dated 22 November 2016 (document number C02155180-06) were taken into account.

Following changes as compared to the last protocol version 3.0 a	annly	3.0	version	protocol	last	the	ed to	compa	as	changes	owing	Fol
--	-------	-----	---------	----------	------	-----	-------	-------	----	---------	-------	-----

The following changes were made based on an FDA Advice Letter dated August 14, 2017 regarding the first signed version of this Trial Statistical Analysis (SAP) dated May 5, 2017. These revisions were accepted by the FDA on November 09, 2017.

- 1. Study populations (Section 6.3) and censoring methods (Section 6.8.3) were separated and described separately to add clarity on the planned analyses. Sections 6.2, 7.4.3, 7.4.4, and 7.6.1 were updated accordingly.
- 2. The censoring rules in Section 6.8.3 were clarified and dates not expected to occur after the date of trial completion (e.g. laboratory sampling or ECG measurements) are not taken into account for censoring.

In addition, the following minor changes have been made version.

to the first signed TSAP

#### 5. ENDPOINTS

The trial is set up with prospective centralized blinded adjudication of cardiovascular, cerebrovascular and renal trigger events. The prospectively defined adjudication process will assess cardiac, neurological, vascular and renal events through independent, blinded, external Clinical Event Committees (CEC).

Additionally, two separate independent, blinded, external committees were set up for adjudication of pancreatic events and assessment of oncological events, respectively.

Definitions of endpoints to be adjudicated and details on the composition of the committees, their procedures and interactions for all events (cardiovascular, cerebrovascular, renal, pancreatic and oncological events) are provided in the CEC charter.

Throughout the SAP the term 'adjudicated' means 'by adjudication confirmed'. The analyses of primary and key secondary endpoint are based on adjudicated events.

#### 5.1 PRIMARY ENDPOINT

The primary endpoint is time to the first occurrence of any of the following by adjudication confirmed components of the primary composite endpoint (3-point major adverse cardiovascular events (MACE)): CV death, non-fatal MI or non-fatal stroke.

This endpoint will also be further referred to as time to 3-point MACE, or shortly 3P-MACE.

#### 5.2 SECONDARY ENDPOINTS

#### 5.2.1 Key secondary endpoint

The key secondary endpoint is time to the first occurrence of any of the following by adjudication confirmed components: renal death, sustained end stage renal disease (ESRD) or sustained decrease of 40% or more in eGFR from baseline. This endpoint will also be further referred to as composite renal endpoint 1.

#### 5.2.2 Secondary endpoint

Not applicable as no secondary endpoint other than the key secondary endpoint is defined for this study.

### 6. GENERAL ANALYSIS DEFINITIONS

#### 6.1 TREATMENTS

[figure not shown]
The following treatments are investigated in this trial:

Table 6.1: 1 Treatments and labels used in the analysis

Tre	eatment	Short label
A	Linagliptin 5 mg	Lina
В	Placebo	Placebo

Study intervals are defined in the following figure:

Figure 6.1: 1 Study intervals

Refer to Section 6.6, in case of missing information in eCRF.

During the study treatment phase, patients are allowed to go off trial medication and subsequently re-start trial medication. This may not happen or may happen repeatedly for a given patient, as this trial is expected to go on for a number of years. This is reflected by the off-treatment phase.

For specific safety and efficacy parameters, the duration of the on-treatment phase is given in Section 6.7.2 and Section 7.8.1.1.

Patients will be analysed as randomized for all analyses (safety and efficacy).

#### **6.2** IMPORTANT PROTOCOL VIOLATIONS

Data discrepancies and deviations from the CTP will be identified for all patients randomized and/or treated.

A protocol violation (PV) is defined as important, if it affects the rights or safety of the trial patients or if it can potentially influence the primary endpoint for the respective patients in a way that is neither negligible nor in accordance with the trial objectives.

The category of important PVs, which can potentially influence the primary or key secondary outcome measures, forms the basis for the decision of whether a patient belongs to a patient analysis set.

The following table displays the categories considered to be important protocol violations. If the data indicate further important PVs, this table will be supplemented accordingly, with the latest modification made prior to database lock.

The important PVs will be described in the Clinical Trial Report (CTR). A listing of patients who had the medication code broken will be provided.

A table showing the number of patients and frequency with violation of in- or exclusion criteria will be provided.

Table 6.2: 1 Important Protocol Violations

Category / Code		Description	Comment/Example	Affects rights (R)/ safety (S) or primary/ key secondary outcome (E)	Excluded from
A		Entrance Criteria Not N			
	A.1	Inclusion criteria violate			
	A1.1	No type 2 diabetes	Inclusion criterion IN1 ticked "No"	Е	PPS
	A.2	Exclusion criteria violat	ted		
	A.2.1	Type I diabetes	Exclusion criterion EX1 ticked "Yes"	Е	PPS
	A.2.2	Severe renal impairment (eGFR < 15 ml/min/1.73 m²) or ESRD at Visit 1 and/or the need for maintenance dialysis	Exclusion criterion EX4 ticked "Yes" Or eGFR < 15 ml/min/1.73 m² at visit 1	Е	PPS
	A.2.3	Pre-planned coronary artery re-vascularisation (PCI, CABG)	Exclusion criterion EX6 ticked "Yes"	Е	PPS
	A.2.4	Specific exclusion criterion for premenopausal women violated	Exclusion criterion EX10 ticked "Yes"	R/S	None

Table 6.2: 1 Important Protocol Violations (cont.)

Cate Cod	egory / e	Description	Comment/Example	Affects rights (R)/ safety (S) or primary/ key secondary outcome (E)	Excluded from
	A.2.5	Patients considered unreliable by the investigator for safe participation in the study	Exclusion criterion EX11 ticked "Yes"	Е	PPS
	A.2.6	Acute coronary syndrome (ACS), diagnosed ≤ 2 months prior to Visit 1	Exclusion criterion EX12 ticked "Yes"	Е	PPS
	A.2.7	Stroke or transient ischemic attack (TIA) ≤ 3 months prior to Visit 1	Exclusion criterion EX13 ticked "Yes"	Е	PPS
В	Γ	Informed Consent			
	B1	Informed consent not available	Inclusion criterion IN7 ticked "No" Or Date of informed consent missing Or No signature on patient's "Declaration of Informed Consent" (to be identified by CRA)	R/S	All

Table 6.2: 1 Important Protocol Violations (cont.)

Cate	egory / le	Description	Comment/Example	Affects rights (R)/ safety (S) or primary/ key secondary outcome (E)	Excluded from
	B2	Informed consent given too late	Date of informed consent for the study not obtained prior to any study related procedure  Minimum requirement for initial informed consent ≤ date of visit 1/date of any study procedure	R/S	None
C		Trial medication and	randomisation		
	C1	Incorrect Trial Medication Taken			
	C1.1	No study medication taken	Patient randomised, but no study medication taken	Е	PPS, TS

Table 6.2: 1 Important Protocol Violations (cont.)

Category / Code	Description	Comment/Example	Affects rights (R)/ safety (S) or primary/ key secondary outcome (E)	Excluded from
C1.2	Randomisation not for	Wrong medication (different medication than the patient was randomised to) taken for more than 20% of the overall treatment duration (between randomisation and first outcome event) of a patient.  This is identified by the medication kit number recorded in eCRF as well as the medication kit number as assigned by IRT.  Can also be manually identified by investigator or CRA.  Can only be finally judged after DBL since unblinding information is required.	E	PPS
C2.1	Treated before randomisation	Date of randomisation after date of study medication intake at visit 2; Or Patient treated according to eCRF, but not randomised according to IRT.	Е	PPS
C3	Non-compliance	-		

Table 6.2: 1 Important Protocol Violations (cont.)

Cat		Description	Comment/Example	Affects rights (R)/ safety (S) or primary/ key secondary outcome (E)	Excluded from
	C3.1	Non-compliance with criteria for removal from the trial	A missing pregnancy test does not qualify as IPV.	R/S	None
D		Concomitant Medication	Not Applicable		
E		Missing data	Not Applicable		
F		Incorrect timing	Not Applicable		
G		Trial specific protocol violations			
	G1.1	Previous participation (randomisation) within this study		E/S/R	PPS
	G1.2	Serious non- compliance potentially affecting primary endpoint		E/S/R	PPS*

Note: Missing visits, evaluations, and tests will be considered missing data, not protocol deviations

\*These patients might be kept out of some further patient analysis sets. The details are described in a separate document.

TSAP for BI Trial No: 1218.22 Proprietary confidential information © 2017 Boehringer Ingelheim International GmbH or one or more of its affiliated companies

#### 6.3 PATIENT SETS ANALYSED

#### **Screened Set (SCR):**

The Screened (Enrolled) Set will include all patients who signed the informed consent.

#### **Randomized Set (RS):**

All screened patients who were randomized, whether treated with trial medication or not.

#### • Treated Set (TS):

All patients treated with at least one dose of trial medication. If no trial medication is taken at site during the visit, but the medication kit was dispensed to the patient and not all trial medication has been returned, the patient will be included in the TS. The TS is the basis for the primary efficacy and the safety analyses.

The following table defines for each planned analysis, which patient set is to be used.

Table 6.3: 1 Table specifying patient sets for analyses

	Patient Sets		
Endpoint	SCR	RS	TS
Disposition	X		
Patient analysis sets		X	
Primary/Key secondary endpoint			X

Other safety endpoints as per Section 5.3.2	X
Post stroke functional assessment as per	X
Section 5.4.1	

\* Sensitivity analysis

Note that the number of patients with available data for an endpoint may differ. For details, see Section 6.6.

^ Demographic analyses will be repeated on the randomised set for EudraCT purposes.

## 6.5 POOLING OF CENTERS

As stated in the CTP, no center effect is included into the model, as the center size is usually expected to be rather small. Furthermore, due to the anticipated low event rate a sufficient number of events per center for the analysis of a center effect and a center by treatment interaction are not expected.

## 6.6 HANDLING OF MISSING DATA AND OUTLIERS

Every effort will be made to collect data as complete as possible. The rules given below are the planned methods for imputation depending upon the type of the endpoint.

For each time to event analysis, patients who do not have a particular outcome will be censored (for details, refer to Section 6.8).

# Partial or missing dates and times

*Non-fatal outcome events* 

In the unlikely case that only the year is documented, the day and month will be imputed as 01 Jan unless the subsequently derived date is before randomisation; in this case the date of randomisation will be used as start date. If year and month is present the day will be imputed as first of the month unless the subsequently derived date is before randomisation; in this case the date of randomisation will be used.

Adverse event (AE) data

Beforehand the missing or partially missing date of first drug administration is imputed. For the handling of AE partial and missing dates the following definitions will be used:

First possible = first possible date of an incomplete AE date

- if only month and year are given: day is set to 1
- if only year is given: day is set to 1 and month is set to January

Last possible = last possible date of an incomplete AE date

- if only month and year are given: day is set to the last possible day of the month
- if only year is given: day is set to 31 and month is set to December

The imputation must be performed in the following order:

- 1) Imputation of completely missing AE end dates
- 2) Imputation of missing/partial AE onset dates
- 3) Imputation of partial AE end dates

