## FLOW CHART

Trial period	Screening	Treatment period						FU
		2	3	4	5	6 to N	EOT C	
Visit	1							
Week	-2	0	12	36	60	84 to N B	-	-
Days from randomization	-14 A	0	84	252	420	588 to N B	-	EOT + 30
Time window (days) O	+13 A		±7	±14	±14	±14	±14	+7
Informed consent	X							
In/exclusion criteria	X	X						
Medical history/ concomitant diagnoses	X							
Demographics	X							
Physical examination F		X		X		X	X	X D
Vital signs	X	X	X	X	X	X	X	X D
Height	X E							
Weight	X E			X	X	X	X	
Waist circumference		X		X	X	X	X	
12-lead-ECG H		X		X	X	X	X	X D
Pregnancy Test I		X		X	X	X	X	
Fasted home blood glucose monitoring J		X	X	X	X	X	X	
Safety laboratory K	X	X	X	X	X	X	X	X D
UACR Q	X	X A		X		X K	X	X D
HbA 1c	X	X	X	X	X	X	X	
Lipid panel		X		X		X K	X	X D
eGFR L	X	X	X	X	X	X	X	X D
Pharmacogenetic sampling P		X						
Adverse events/outcome events M	X	X	X	X	X	X	X	X
Concomitant therapy	X	X	X	X	X	X	X	X
Randomization (IRT) N		X						
Dispense study medication (IRT) N		X	X	X	X	X		
Return study medication/ medication compliance check			X	X	X	X	X	

Proprietary confidential information.

© 2016 Boehringer Ingelheim International GmbH or one or more of its affiliated companies. All rights reserved.

This document may not - in full or in part - be passed on, reproduced, published or otherwise used without prior written permission.

Flow Chart (continued)

A Randomization may be done as soon as the visit 1 (safety) laboratory results and eGFR are known and all other eligibility criteria are met. If the UACR result at visit 2 is required to fulfil inclusion criterion 8, randomization may be postponed until the laboratory results are known. It's not required to repeat visit 2 assessments if the patient returns to the clinic for randomization.

B A clinic visit will be scheduled every 24 weeks until study end.

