### 3.3.4 Removal of patients from therapy or assessments

#### 3.3.4.1 Removal of individual patients

This is a long-term safety **outcome** study **and every effort should be made by the site staff to encourage patients to remain in the study and on study drug if medically safe.**

Patients who discontinue study drug prematurely should be observed until study end **as if they were still receiving blinded study treatment**. Patients who prematurely discontinue study drug **should** remain in the study. Study assessments may be omitted if a patient is willing to return to the pre-defined study visits, with exception of **adverse events, outcome events, concomitant therapy and laboratory testing of creatinine for the calculation of the eGFR.**

If a patient who prematurely discontinued study drug is not willing to return at the pre-defined regular visit schedule, at minimum a yearly telephone call (preferably every 6 months) and a telephone call at study end will be **asked for required**, to document the occurrence of outcome events and vital status. If possible, also other AE's and concomitant therapy changes since last visit **might should** be recorded. Every attempt will be made by the investigator to ensure patients continue participating in the study during study drug interruptions and after discontinuation of study drug.

Patients who prematurely discontinue study medication **during the treatment phase** are allowed to restart the study medication at any time if appropriate in the opinion of the investigator and if not contraindicated. In this study, patients are allowed to have multiple study drug interruptions. There is no limit on either the number of study drug interruptions or the maximum length of any study drug interruption. **Investigators should routinely consider re-starting study drug at every visit following study drug discontinuation.**

**A patient should be instructed to stop the study drug only after discussion between sponsor representative and investigator, if eligibility criteria are being violated, or if the patient fails to comply with the protocol (e.g. non-attendance at study assessments).**

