#### **6.8.2** Date of event

For composite outcomes, e.g. time to first 3P-MACE, the earliest onset date of the corresponding components will be used

The dates determined by the adjudication committee will be used; these can be different from the investigator reported dates.

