## 6.8.3 Censoring

Primary endpoints

The underlying principle is that the censoring date should be the date at which the patient was last known to be free of an endpoint event (e.g. free of each component of the 3P-MACE).

Patients without occurrence of a specific endpoint (composite endpoint or individual components) will be considered censored at the individual day of trial completion\*.

- \* This is defined as the latest of the following dates as of
  - adverse event/outcome event start dates (if non-fatal event),
  - onset dates of adjudicated (by adjudication confirmed and non-confirmed) events (if non-fatal event),
  - date of trial completion (defined as latest of date of last clinic visit, last telephone contact, date of last contact if lost to follow-up).

For patients who died during the study, the date until which follow-up for non-fatal outcome events was performed will be used for censoring.

Censoring is considered independent from trial drug intake.

Generally, the 7 days censoring definition will be used for adverse events incl. hypoglycaemia.

All of the above mentioned x-day censoring rules will be handled as follows:

Patients who did not experience the event will be censored at the earliest date between the individual day of trial completion (defined above) and x days after last intake of study drug. For this analysis events will be considered that occurred not later than x days after last intake of study drug, or until individual day of trial completion (defined above), whichever is earlier.

Endpoints based only on laboratory data (by adjudication confirmed or not)

Patients who already fulfil the respective condition at baseline are generally not considered in the number of patients at risk for this endpoint (

If a baseline laboratory measurement is not available for the parameter of interest, it is assumed that the patient did not experience the condition corresponding to the endpoint at baseline and the patient is included in the patients at risk for this endpoint.

Patients without an event and available post-baseline laboratory measurements will be considered censored at the date of last laboratory sampling of the corresponding parameter. Patients with missing baseline laboratory required to derive a change from baseline and patients without laboratory data following the baseline measurement will be censored on the day of randomisation or date of first study drug intake, respectively.

Page 51 of 80

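### SAP 6.6 can date a partially dated non-fatal event before an event-free contact: negligible for the primary hazard ratio, but TS+30 can then count a post-window event as on-treatment

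*SAP*

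**What the plan says.** SAP 6.6, under partial or missing dates, covers non-fatal outcome events in two sentences. For a year-only date: "In the unlikely case that only the year is documented, the day and month will be imputed as 01 Jan". The one exception is a result that would fall earlier than randomisation, which is moved up to the randomisation date. For a date with month and year: "If year and month is present the day will be imputed as first of the month", with the same randomisation exception. No bound refers to the last event-free contact, to the stop of study drug or to the date of the report.

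SAP 6.8.2 takes event dates from adjudication: "The dates determined by the adjudication committee will be used; these can be different from the investigator reported dates". For composites, "the earliest onset date of the corresponding components will be used". It does not say whether the 6.6 rule acts before or after adjudication, or whether the committee must supply a full date.

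SAP 6.8.3 handles patients without an event. Its principle is that "the censoring date should be the date at which the patient was last known to be free of an endpoint event". The same section says that an x-day analysis counts only events dated no later than x days after last intake. Protocol 7.3.1 plans such an analysis, TS+30, as a sensitivity analysis for the primary and key secondary endpoints.

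On contacts, the protocol flow chart has visits at weeks 12, 36, 60 and 84, and its footnote B says "A clinic visit will be scheduled every 24 weeks until study end". Outcome events are recorded at each visit, including the follow-up visit 30 days after end of treatment. Patients off drug who will not attend get "at minimum a yearly telephone call (preferably every 6 months) and a telephone call at study end" (Protocol 3.3.4.1).

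**The concern.** Suppose a patient is seen in June without an event, and a stroke later that year is known only by its year. The rule dates the stroke to 1 January, before a visit that shows the patient had not yet had it. The SAP uses knowledge of event-free status to place censoring dates but not to place partial event dates. Elsewhere in 6.6, visit information does bound imputed dates: partial end dates of adverse events in surviving patients are capped at the last visit.

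Two things could be at stake. The first is event times in the primary Cox model. The second is classification in TS+30, where moving an event back can change whether it is counted at all. TS+30 is there to look at events close to drug exposure. If a drug effect fades after stopping, admitting later events would dilute what that analysis is meant to show.

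**Working it through.** **1. Design figure.** Inputs from Protocol 7.1 and 7.6: margin 1.3, true hazard ratio 1, one-sided 2.5%, power 90%, 1:1 allocation. Events = 4 × (1.960 + 1.282)² / (ln 1.3)² = 42.03 / 0.0688 = 610.6, so 611, as the protocol states. Power with 611 events is 90.0%. The date rule does not change the number of events in the primary analysis, so it leaves this figure alone.

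**2. Size of the shift by hand, ignoring the randomisation bound.**
- Year-only, event uniform over the year: mean shift (0 + 364)/2 = 182 days. With visits every 168 days, the chance that a visit lies between 1 January and the event is (168 × 0.5 + 197 × 1)/365 = 281/365 = 0.77. With a single yearly call it is 0.50.
- Month-only, 30-day month: mean shift (0 + 29)/2 = 14.5 days. The chance of an intervening visit is about 14.5/168 = 0.09.

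**3. The same with the randomisation bound and the actual schedule.** Simulation of 400,000 event dates, uniform over follow-up, with 36-month recruitment, a 54-month trial, and visits at days 84, 252 and every 168 days after.

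| Known part of date | Mean shift (days) | Maximum (days) | Before ≥1 event-free visit | Before ≥2 |
|---|---|---|---|---|
| Year only | 171 (median 166) | about 365 | 74% | 27% |
| Year and month | 14.6 | 30 | 8% | 0% |

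Of the year-only events, 19% are reset to the randomisation date, which is why the mean is below 182 days.

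**4. Effect on the primary hazard ratio.** Simulated trials of 7000 patients with a hazard of about 0.031 per year, set to give 611 events at hazard ratio 1. Cox model with Breslow ties, treatment only, 400 trials per scenario. Year-only scenarios were run at true hazard ratios 1.0 and 1.3, month-only scenarios at 1.0. The share of partial dates is an assumption, since neither document gives one.

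| Assumed partial dates | Change in mean hazard ratio | Largest change in any trial | Non-inferiority conclusions changed |
|---|---|---|---|
| Year-only, 1% or 5%, both arms | below 0.01% | 0.14% | 0 of 400 |
| Year-only, 5%, one arm only | about 0.1% | 0.23% | at most 1 of 400 |
| Year-only, 20%, one arm only | about 0.3% | 0.51% | at most 2 of 400 |
| Month-only, 5%, one or both arms | below 0.01% | 0.06% | 0 of 400 |

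For scale, 1% and 5% of 611 are about 6 and 31 events.

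**5. When TS+30 is affected.** An event is counted if its imputed date is no later than last intake + 30 days. A year-only event after the window is wrongly counted if last intake + 30 days falls on or after 1 January of the event year. Last intake on 2 December just meets this, since 2 December + 30 days = 1 January. Example: last intake 10 December, window closes 9 January, stroke the following September with only the year known. The rule dates it to 1 January and TS+30 counts it. For a month-only event the condition is that last intake + 30 days falls on or after the 1st of the event month. If the window closed in an earlier calendar year (or month) than the event, nothing changes.

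**6. With a lower bound at the last event-free visit.** The year-only mean shift falls from 171 to 69 days and the maximum from about 365 to 168. Month-only goes from 14.6 to 13.8 days. If the follow-up visit 30 days after end of treatment took place and was event-free, the day after it lies beyond last intake + 30 days, so the error in step 5 cannot occur for that patient.

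**The case against.** The strongest objection is reach. The analysis uses the committee's dates, and the charter that would show whether these are always complete is not among the documents. If they are, the rule never touches an adjudicated MI or stroke. This stands as a limit on the point, but the SAP does not itself say so.

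Partial dates should also be rare. The SAP calls the year-only case unlikely. Outcome events must be documented within 24 hours of awareness (Protocol 5.2.2.2), source documents are pursued for adjudication triggers (8.3.1), and the Rankin score is timed from stroke onset (5.3.2). This stands too.

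The rule is prespecified and identical in both arms, and in a safety trial leaning towards on-treatment attribution can be defended. That is fair as a choice, but the SAP does not give it as its reason, and the rule still overrides recorded information.

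An uneventful contact does not prove that no event had occurred, because a vaguely dated event may have gone unreported at the time. This is why the bound should use contacts documented free of that event and be capped at the last possible date.

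Finally, TS+30 is only a sensitivity analysis, and parts of the SAP that bear on it (7.4.3, Table 6.7.2: 1, some of 6.8.3) are not in the public text. Further handling there cannot be excluded.

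**Conclusion.** The point holds as a minor, nearly free improvement. The rule as written can place an event before a contact that shows the patient free of it: about 74% of year-only and 8% of month-only events, assuming uniform event timing and visits on schedule. The consequence worth acting on is misclassification in TS+30, under the calendar condition in step 5 and only where the adjudicated date is partial. Its frequency is unknown.

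A reader might infer more, and the documents do not support it:
- That the primary analysis is biased. Affected event times do move early, but each event still counts once, the rule is the same in both arms and the Cox model uses only the order of times. The simulated effect is negligible even at shares well above what the SAP's wording suggests.
- That 6.6 contradicts 6.8.3. The last-known-free principle governs censoring of patients without an event; it is not a rule for dating events.
- That a definite number of events is affected. A share of 0.5% to 2% of 611 would give 3 to 12, but that share is an assumption.
- That partial dates cluster in off-drug patients followed by yearly calls. This is plausible, but no section says so.

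**What to change.** Replace the rule in SAP 6.6 for non-fatal outcome events with one that applies only where the adjudication committee gives no full date:

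imputed date = min{ max(first possible date, randomisation date, day after the last contact documented free of that event), last possible date, report date }.

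Add that the number of imputed event dates will be reported by arm, split into year-only and month-only, and state in 6.8.2 that the rule acts after adjudication.

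The cost is about two sentences and one derivation step. The 611 events and the 90% power are unchanged. The protocol already has outcome events assessed at visits and calls, so no new collection should be needed. The documents do not show how event-free status is stored for each contact, so programming should confirm this before the text is final.
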